6. STUDY DESIGN

This is a prospective, single arm, non-randomized, multi-center observational study to record objective data in patients undergoing upper extremity arteriovenous fistula construction with autologous tissue for the purpose of eventual hemodialysis access, in whom the EchoMark implantable marker is placed at the site of vascular anastomosis and the EchoSure module is used to collect ultrasonic data.

The expected duration of this study will be from May 2020 to December 2021. Patients will be identified and recruited by the surgeons participating in the study, who will be determined at a later date. Patients who have been scheduled for creation of an upper extremity autologous arteriovenous fistula creation surgery will be identified as appropriate for study recruitment. The study details will be explained to identified patients and the consent process will begin for willing patients. Participants in the study will have EchoMark devices implanted at the time of the surgery. Monitoring of fistulae will be performed in the postoperative period. Patients who wish to terminate their participation in the research will no longer receive EchoSure ultrasound examinations of their fistula and will revert to the standard monitoring practice of their surgeon.

Stage 1: Patients will be monitored using the EchoSure ultrasound to collect data. Data will be analyzed in an attempt to formulate normative ranges for relevant variables such that clear, objective metrics consistent with healthy versus pathologic fistula healing are established.

Stage 2: Patients will be monitored via EchoSure ultrasound in addition to the standard of care currently followed by the surgeon. Decisions will be made by the vascular surgeon, using a combination of clinical data and the EchoSure data to determine if and when interventions need to be made to prevent failure of fistula maturation. We will then calculate the effect of the EchoMark and EchoSure on the rate of successful fistula maturation.

With the implantation of any foreign material such as a radiologic marker (EchoMark), there is some risk of infection, inflammation or extrusion. Given the biocompatibility data collected by the company and the extensive prior use of the material in medicine, the probability of such risk is extremely low and has already been evaluated by the FDA during the approval process for EchoMark. There is risk that the ultrasound scan may create mild discomfort for the patient on the wound site. The likelihood and severity of this risk is low. If the patient begins to exhibit signs of infection, inflammation or extrusion, a clinical decision will be made by the team if the risk from the implantable device requires removal of the device. In these cases, the implantable device will be removed, and the patient will be monitored with conventional methods.

If ultrasound scanning is found to create discomfort to patient that exceeds that of traditional monitoring devices such as standard ultrasonography, the patient will be offered the option of discontinuation of EchoSure ultrasound scans and be monitored subsequently with conventional methods.

Despite the significant benefit of fistula surgery, there remains a significant risk of postoperative thrombosis, inappropriate fistula maturation, and continued reliance on prosthetic central vascular access for hemodialysis, all of which can cause serious morbidity and even mortality. By using this technology, it is possible that impending failure of fistula maturation can be detected early enough to salvage the fistula and prevent the impending fistula failure and associated morbidity.

Should the patient opt out of the study, they will be monitored with the current standard of care within the vascular surgeon's practice. This includes clinical observation and color Doppler ultrasonography per the surgeon's standard practice.

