3. STUDY SUMMARY

Title:	Automated Ultrasound Flow Monitoring for Maturation of Peripheral Arteriovenous Fistulae
Protocol Number:	2019-1
Design:	
This is a prospective, single arm, non-randomized, multi-center observational study to demonstrate the performance of the EchoMark and EchoSure devices in patients undergoing peripheral arteriovenous fistula creation for hemodialysis access.
 
Stage 1: EchoMark implantation at the time of fistula creation with scheduled follow up for EchoSure imaging of the fistula maturation process. This stage will produce EchoSure criteria for early prediction of maturation failure.
 
Stage 2: EchoMark implantation and imaging with EchoSure to prove the robustness of the fistula maturation failure criteria established in stage 1 and measure the effect on ultimate fistula maturation rates.

Study Duration:	
Projected enrollment of first patient: May 2020
 
Projected exit of final patient: December 2021

Primary Objective:	
Stage 1: The primary objective of the study is to collect data to verify the technology's performance in monitoring fistula maturation and understand the natural history of AV fistula flow physiology.
 
Stage 2: The primary objective of the study is to assess the ability of the EchoMark and EchoSure system to reduce the rate of failed fistula maturation.

Patient Population:	Patients undergoing upper extremity autologous arteriovenous fistula creation.
Sample Size:	
Stage 1: Up to sixty (60) patients will be enrolled.
 
Stage 2: Up to sixty (60) patients will be enrolled.

Number of Sites:	To be determined
Treatments:	
Stage 1: EchoMark soft tissue marking devices will be placed and monitored using the EchoSure system for 24 weeks or confirmed fistula maturation/failure has been declared by the attending vascular surgeon, whichever comes first.
 
Stage 1: EchoMark soft tissue marking devices will be placed and monitored using the EchoSure system for up to 52 weeks. Upon the decision by the attending surgeon that the fistula failure is confirmed or that monitoring is no longer clinically necessary patients will exit the study

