5. STUDY OBJECTIVES

Purpose

Stage 1: The primary objective of Stage 1 of the study is to collect data to verify the technology's performance in fistula monitoring. In Stage 1, EchoMark is implanted and monitoring is completed post-operatively. EchoSure data is then captured in an effort to establish normal ranges of the relevant variables in the context of appropriately maturing fistulae and their physiology, which is currently unknown.

Stage 2: The purpose of Stage 2 of the study is to evaluate the performance of the EchoMark and EchoSure (both FDA approved devices) as an ultrasound-based method of monitoring maturation of fistulae. The implant and ultrasound will be used as per IFU. The primary purpose of the study is to collect data on patient outcomes and assess whether or not the information generated from use of

EchoMark and EchoSure can decrease the fistula maturation failure rate and improve the patency of fistulas after up to a year.

Performance Goals

Stage 1:

Primary Performance Endpoint:

- Data collection to verify accuracy
- Data collection to understand the natural history of flow physiology in AV fistulas and classify fistulas that will fail

Primary Safety Endpoint:

- Procedure freedom from Serious Adverse Events (SAEs) during the EchoMark implantation procedure and subsequent post-operative period

Stage 2:

Primary Performance Endpoint:

- Failed fistula maturation rate

Secondary Performance Endpoints:

- Cumulative fistula patency at the end of 1 year
- Volumetric flow data
- Vessel caliber
- Total cost of episode of care

Primary Safety Endpoint:

- Procedure freedom from Serious Adverse Events (SAEs) during the EchoMark implantation procedure and subsequent post-operative care.

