For this portion of the study, we will recruit an additional 60 patients planning to undergo elective construction of upper extremity autogenous hemodialysis access. Again, the EchoMark fiducial marker will be inset at the time of fistula creation. The minimum sample size of 45 (60 prior to 25% dropout factor) is powered to detect an approximate 25% reduction in all-cause fistula failure in the early postoperative period. A χ^2 power analysis was performed with $\alpha = 0.05$, $\beta = 0.8$ and standard-of-care fistula maturation success at 50% based on institutional experience and prior literature which ranges from 30-70% and EchoSure early intervention success based on the Muray-Cases results which showed a 78% success rate achieved by a novel program of pre-maturation ultrasonography and early intervention.

The nominal-by-interval association coefficient, Eta, will be calculated to determine the correlation between successful, unassisted maturation and EchoSure-derived values for flow and conduit diameter at two weeks. This will be compared to the similar findings of stage 1 using Student's t-testing and will validate the early maturation criteria derived from there. The association coefficient will be calculated to determine the correlation between successful, assisted maturation and EchoSure-derived values for flow and conduit diameter immediately following intervention. Pearson's correlation will be performed on both EchoSure-derived and Duplex-derived values of volumetric flow and conduit diameter to determine correlation between findings immediately following intervention and those at six weeks. [REDACTED]

Using χ^2 testing between the stage 1 and 2 cohorts, the benefit to maturation success of intervention based on early postoperative EchoSure examination will be determined.

9: PATIENT ENROLLMENT AND CONSENT

Method of Subject Identification and Recruitment

Patients will be identified and recruited by the surgeons participating in the study. Patients who have been scheduled for a fistula creation surgery will be identified as appropriate for study recruitment. The study details will be explained to identified patients and the consent process will begin for willing patients.

Informed Consent

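### Both stages use EchoMark and EchoSure, so the Stage 1 versus Stage 2 test cannot give the effect of the device system on maturation that Sections 3 and 6 promise

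*Combined protocol and SAP*

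**What the plan says.** **The broad statement.** Section 3 (Study Summary) gives the Stage 2 primary objective as to "assess the ability of the EchoMark and EchoSure system to reduce the rate of failed fistula maturation". Section 6 (Study Design, Stage 2) closes with "We will then calculate the effect of the EchoMark and EchoSure on the rate of successful fistula maturation".

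**Who receives the devices.** Section 3 describes "Stage 1: EchoMark implantation at the time of fistula creation with scheduled follow up for EchoSure imaging of the fistula maturation process". Section 5 confirms it: "In Stage 1, EchoMark is implanted and monitoring is completed post-operatively". Section 6 adds: "Stage 1: Patients will be monitored using the EchoSure ultrasound to collect data". Section 8 has the marker placed again in Stage 2, and Section 6 has Stage 2 patients scanned on top of the surgeon's usual care. The study is described as single arm and non-randomized.

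**What Stage 2 adds.** According to Sections 6 and 10, it adds the values derived in Stage 1 and the surgeon's use of EchoSure flow data when deciding on intervention.

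**The test.** Section 8 (Stage 2) plans chi-square "testing between the stage 1 and 2 cohorts, the benefit to maturation success of intervention based on early postoperative EchoSure examination will be determined". Section 5 similarly asks whether the information produced by the devices can lower the failure rate. Both are narrower than the wording in Sections 3 and 6.

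**The planning rate.** Section 8 (Stage 2) takes "standard-of-care fistula maturation success at 50" per cent against 78% with early intervention. Section 8 (Stage 1) makes the Stage 1 cohort the planned comparator and assumes 50% maturation in it.

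**The concern.** A comparison of two groups cannot estimate the effect of something both groups receive. Here that applies to the marker and to the scanning. The contrast can speak at most to what Stage 2 adds, namely acting on the readings with the Stage 1 criteria. A larger sample would not change this, and nor would strict withholding of Stage 1 readings from surgeons.

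Two consequences follow. First, a reader who takes the Section 3 objective and the Section 6 sentence at face value could treat a positive chi-square as evidence that the system improves on standard care, which this design cannot show. Second, the standard-of-care label on the 50% rate hides an assumption: that a cohort with the marker and scans will mature at the same rate as patients with neither. If that assumption fails, the planned power fails with it.

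**Working it through.** **1. Exposure by stage (Sections 3, 5, 6, 8 and 10)**

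| Component | Stage 1 | Stage 2 | Device-free cohort |
|---|---|---|---|
| EchoMark implanted | yes | yes | not planned |
| EchoSure scans | yes | yes | not planned |
| Stage 1 criteria and surgeon's planned use of flow data | no | yes | not planned |

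Only the last row differs by plan. The stages are also sequential, so calendar period and case mix may differ.

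**2. What the stage difference estimates**

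Let *p0* be maturation under standard care without the devices, *m* the additive effect of marker plus scanning, *u* the effect of acting on the readings, and *t* any period or case-mix shift.

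- Stage 1 rate = *p0* + *m*
- Stage 2 rate = *p0* + *m* + *u* + *t*
- Stage 2 minus Stage 1 = *u* + *t*, so *m* drops out
- System against standard care = *m* + *u*

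Take *p0* = 50% and *u* = 78 - 50 = 28 points from Section 8, with *t* = 0. The values of *m* are assumptions.

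| *m* (points) | Stage 1 | Stage 2 | Stage difference | System vs standard care |
|---|---|---|---|---|
| -10 | 40% | 68% | 28 | 18 |
| -5 | 45% | 73% | 28 | 23 |
| 0 | 50% | 78% | 28 | 28 |
| +5 | 55% | 83% | 28 | 33 |
| +10 | 60% | 88% | 28 | 38 |

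The cancellation is exact only because *m* is additive and equal in both stages. If the marker and scanning act as a common odds ratio instead (assumed range 0.67 to 1.5):

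- OR 0.67: Stage 1 40.1%, Stage 2 70.4%, difference 30.3; system vs standard care 20.4
- OR 1.5: Stage 1 60.0%, Stage 2 84.2%, difference 24.2; system vs standard care 34.2

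The stage difference now moves a little, and in the opposite direction to the system effect. It still does not recover it.

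**3. Reproducing the planned sample size**

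Inputs from Section 8: 50% vs 78%, alpha 0.05, 0.8 (written as beta, read as power). Two-sided is assumed because the plan does not say. With pooled variance and no continuity correction:

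n = [1.96 √(2 p̄(1 - p̄)) + 0.842 √(p1(1 - p1) + p2(1 - p2))]² / (p2 - p1)², with p̄ = 0.64

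= [1.96 × 0.6788 + 0.842 × 0.6493]² / 0.28² = 44.9, so 45 per stage.

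Dropout: 45 / (1 - 0.25) = 60. Power at 45 per stage is 80.1%. The arithmetic is sound.

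**4. Power if the Stage 1 rate is not 50%**

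Stage 2 is held at 78%, and the higher Stage 1 rates are assumptions.

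| Stage 1 rate | Difference (points) | Power, 45 per stage | n per stage for 80% |
|---|---|---|---|
| 50% | 28 | 80% | 45 |
| 55% | 23 | 64% | 65 |
| 60% | 18 | 45% | 103 |
| 65% | 13 | 27% | 189 |

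**5. Can Stage 1 be set against 50% instead?**

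Only descriptively. With 22 of 45 matured (an illustrative count close to half), the exact 95% CI is 33.7% to 64.2%. An exact two-sided test against 50% with n = 45 rejects low at 15 or fewer. Its power is 22.5% if the true rate is 40% and 47.5% if it is 35%. Section 8 also cites prior literature ranging from 30% to 70%, so 50% is not a firm benchmark.

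**The case against.** The strongest reply is that the narrower question is already in the plan. Section 8 describes the chi-square as measuring the benefit of intervention based on early EchoSure examination, and Section 5 speaks of information from the devices. On that view Sections 3 and 6 are loose shorthand. This stands in part: the test can address the narrower question, and the defect is an inconsistency. But the broad wording sits in the headline objective and the design statement, which are what most readers will cite.

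Three stronger readings are tempting, and the documents do not support them.

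- *The marker harms maturation and the design hides it.* Section 6 says "there is some risk of infection, inflammation or extrusion", but goes on to call the probability extremely low, and no passage links the marker to poorer maturation. Freedom from serious adverse events is a primary safety endpoint in both stages, so serious harm has its own outcome, although that endpoint does not measure an effect on maturation. The negative values of *m* above are illustrations.
- *The test is sized against the wrong group.* Section 8 (Stage 1) names the Stage 1 cohort as the comparator. The 50% is its planning value, and 45 per stage reproduces. The label and the untested assumption are at fault, not the calculation.
- *The stage difference cleanly measures the effect of surgeons using the readings.* It does not. The stages are sequential and non-randomized. No passage withholds Stage 1 readings from surgeons. Section 7 enrols patients whose surgeon has chosen these devices for monitoring, and Section 10 allows salvage attempts in Stage 1. Period, case mix and leakage of readings all affect the contrast.

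**Conclusion.** The concern holds as an overstated and inconsistent statement of what Stage 2 estimates. The planned test cannot deliver the effect of EchoMark and EchoSure (Section 6), nor show that the system reduces failed maturation against standard care (Section 3), because no group is without the devices. An effect of marker or scanning common to both stages is largely invisible to the test, and wholly so only if it is additive and equal in both. What can be estimated is the difference between stages, which is the question in Sections 5 and 8 subject to confounding and dilution.

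At the assumed additive effects of -10 to +10 points, a 28-point stage difference is compatible with a system effect of 18 to 38 points. The sample size is correct at its stated rates, but power falls to about 64%, 45% or 27% if Stage 1 matures at 55%, 60% or 65% with Stage 2 at 78%. These are assumed rates, not predictions.

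This should be fixed. It changes what the trial may conclude, but the statistical section already points to the right question and no data collection has to change.

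**What to change.** 1. **Sections 3 and 6.** Align them with Sections 5 and 8. State the Stage 2 result as: the difference in maturation between Stage 1 and Stage 2, where Stage 2 adds surgeon use of EchoSure data and the Stage 1 criteria, among patients who all carry EchoMark. Remove the promise to calculate the effect of EchoMark and EchoSure.
2. **Limits of the comparison.** State beside that definition that the difference is non-randomized and sequential, may be confounded by period and case mix, and may be diluted if Stage 1 readings reached surgeons.
3. **Section 8, Stage 2 sample size.** Describe 50% as the assumed maturation rate of the Stage 1 cohort.
4. **Section 8, analysis.** Report the between-stage difference with a 95% CI alongside the chi-square. Report the Stage 1 proportion with an exact 95% CI beside the 50% planning value, labelled descriptive only.

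The cost is protocol and SAP wording plus two intervals from data already planned. No patients, visits or tests are added. The downside is a narrower permitted claim. If the sponsor wants a whole-system effect, wording will not supply it; that would need a comparator without the devices, concurrent or matched historical.

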7. STUDY POPULATION

Number of Patients

Stage 1: Up to sixty (60) patients will be enrolled and both men and women will

be eligible for inclusion. The estimated enrollment period is six months and patients will be followed until the fistula matures and is suitable for use in dialysis or it is ultimately considered non-salvageable by the vascular surgeon.

Stage 2: Up to sixty (60) patients will be enrolled and both men and women will be eligible for inclusion. The estimated enrollment period is twelve months and patients will be followed until then or the decision by the attending surgeon that the fistula failure is confirmed, or that monitoring is no longer clinically necessary patients will exit the study.

Intended Use

The EchoMark and EchoSure devices are intended to be used by a trained medical professional. The EchoMark device is intended to be a Single Use Device, used in a surgical operating suite or equivalent setting. The EchoSure ultrasound devices are reusable and may be used in the operating suite, a post-operative unit such as the ICU or patient floor, or a typical outpatient clinic. When used intraoperatively or in the presence of breached skin, the ultrasound transducer should be used with a sterile probe cover.

Inclusion Criteria

- Age > 18 years
- Patients presenting for upper extremity arteriovenous fistula construction with autologous tissue for the purpose of eventual hemodialysis access where the surgeon has selected EchoMark and EchoSure as the optimal method of vascular monitoring based on clinical assessment and plan
- Patient is able to sign informed consent and able to participate in all testing associated with this clinical investigation
- Women of childbearing potential have a negative pregnancy test

Exclusion Criteria

- Age <18 years old
- Patient unable to sign informed consent
- Patient participating in another investigational device or pharmacological study
- Prisoner or patient from vulnerable populations as defined in 45 CFR 46.

This study will not target the recruitment of any potentially vulnerable subjects. If vulnerable subjects who are educationally or economically impaired present for fistula creation, they will not be given the opportunity to participate in the study.

PATIENT WITHDRAWAL FROM THE STUDY

Patients are free to withdraw consent at any time. Patients who wish to terminate their participation in the research will no longer receive EchoSure ultrasound examinations of their fistula and their data will be removed from the study.

8: STATISTICAL ANALYSIS

Stage 1:

We will recruit 60 patients for participation in this study who are planning to undergo elective construction of upper extremity autogenous hemodialysis access. The minimum sample size of 45 was determined assuming a 50% successful fistula maturation rate (based on past studies) to yield sufficient power to detect a difference in maturation between this cohort and the intervention cohort in the next aim. It also accounts for the quantity of patient volumes needed to develop a [REDACTED] based on our experience with EchoSure. Lastly, this provides sufficient power to detect a difference in fistula maturation success based on the flow rate (logistic regression power estimation; $\alpha = 0.05$, $\beta = 0.8$, OR 2.5 [from $\text{Pr}(H_0) 0.45$ and $\text{Pr}(H_1) = 0.65$]. As a buffer, based on institutional experience with clinical research and subject attrition a drop-out rate of 25% has been added to yield a total of 60 patients.

Using the EchoSure-derived conduit diameter and volumetric flow as observed values and Duplex-derived conduit diameter and volumetric flow as accepted values, the accuracy of EchoSure will be calculated. Logistic regression will be used to assess the correlation between successful maturation and EchoSure-derived values for flow and conduit diameter at two weeks. Cut points will be evaluated to establish EchoSure criteria for [REDACTED] [REDACTED]. Pearson's correlation will be performed on both EchoSure-derived and Duplex-derived values of volumetric flow and conduit diameter to determine correlation between EchoSure findings at two weeks and both EchoSure and Duplex findings at six weeks.

Stage 2:

For this portion of the study, we will recruit an additional 60 patients planning to undergo elective construction of upper extremity autogenous hemodialysis access. Again, the EchoMark fiducial marker will be inset at the time of fistula creation. The minimum sample size of 45 (60 prior to 25% dropout factor) is powered to detect an approximate 25% reduction in all-cause fistula failure in the early postoperative period. A χ^2 power analysis was performed with $\alpha = 0.05$, $\beta = 0.8$ and standard-of-care fistula maturation success at 50% based on institutional experience and prior literature which ranges from 30-70% and EchoSure early intervention success based on the Muray-Cases results which showed a 78% success rate achieved by a novel program of pre-maturation ultrasonography and early intervention.

The nominal-by-interval association coefficient, Eta, will be calculated to determine the correlation between successful, unassisted maturation and EchoSure-derived values for flow and conduit diameter at two weeks. This will be compared to the similar findings of stage 1 using Student's t-testing and will validate the early maturation criteria derived from there. The association coefficient will be calculated to determine the correlation between successful, assisted maturation and EchoSure-derived values for flow and conduit diameter immediately following intervention. Pearson's correlation will be performed on both EchoSure-derived and Duplex-derived values of volumetric flow and conduit diameter to determine correlation between findings immediately following intervention and those at six weeks. [REDACTED]

Using χ^2 testing between the stage 1 and 2 cohorts, the benefit to maturation success of intervention based on early postoperative EchoSure examination will be determined.

9: PATIENT ENROLLMENT AND CONSENT

Method of Subject Identification and Recruitment

Patients will be identified and recruited by the surgeons participating in the study. Patients who have been scheduled for a fistula creation surgery will be identified as appropriate for study recruitment. The study details will be explained to identified patients and the consent process will begin for willing patients.

Informed Consent

Written informed consent, in accordance with applicable international standards and trial center regulations, shall be obtained from each subject, prior to the trial procedures. The investigator retains a copy of the signed informed consent document in each subject's record, and provides a copy to the subject.

The Investigator must obtain the written informed consent of all subjects, and must not allow any subject to participate in the investigation prior to obtaining governing institutional review board (IRB), research ethics board (REB) approval, or Ethics Committee (EC) approval. Before starting the trial, the investigator provides the trial Sponsor with a copy of the sample Informed Consent document approved by the IRB, REB, or EC with documented evidence that the IRB, REB, or EC approved the protocol and the informed consent.

Process of Consent

Patients eligible for the study will receive detailed written information on the trial, after which they will be asked to give *written* informed consent in accordance with the local clinical site's Ethics Committee. **Oral consent is not an acceptable substitute.**

Consent may only be obtained in person by a member of the study team delegated with consenting responsibilities. Consent will be obtained by a member of the research team in the patient's preoperative visit to clinic or in the pre-operative area prior to the initiation of anesthesia. The research team will take as much time as necessary to confirm full understanding of the study in the consent discussion. There will be sufficient time for the patient to consider the

study obligations and decide whether or not to participate, as study participation will not change clinical care and their data can be removed at any time if they choose to disenroll. Participation is fully optional.

Study personnel should explain that even if a patient agrees to participate in the study and signs the ICF, the patient may not be eligible to participate if he/she fails additional eligibility criteria or the surgical plans changes during the procedure.

Once signed, a copy of the Patient Informed Consent document and the Patient Information Sheet will be given to the patient.

A Screening and Enrollment Log will be maintained in the on-site clinical records located at the study site to document select information about candidates who are enrolled in the study as well as those who fail to meet the entry criteria.

Vulnerable Subjects

This study will not specifically target the recruitment of any potentially vulnerable subjects. If a patient from a vulnerable population presents for a fistula creation procedure, they will not be given the option to participate in the study.

Study Enrollment

Patients will be considered enrolled in the trial once informed consent has been obtained and all eligibility criteria confirmed.

